## 7. PLANNED ANALYSIS

The format of the listings and tables will follow the BI guideline "Reporting of clinical trials and project summaries" (001-MCG-159) ([10](#)).

The individual values of all patients will be listed. Listings will generally be sorted by country, centre number, patient number and visit (if visit is applicable in the respective listing). AE listings will be sorted by assigned treatment (see [Section 7.8.1](#) below for details). The listings will be contained in Appendix 16.2 (SDL) of the CTR.

Analyses of secondary and further PK endpoints will be performed by BI and presented in Section 15.6 of the CTR.

The following standard descriptive statistical parameters will be displayed in summary tables of continuous variables:

N	number of non-missing observations
Mean	arithmetic mean
SD	standard deviation
Min	minimum
Q1	lower quartile
Median	median
Q3	upper quartile
Max	maximum

For plasma concentrations as well as for all PK parameters, the following descriptive statistics will additionally be calculated:

CV	arithmetic coefficient of variation
gMean	geometric mean
gCV	geometric coefficient of variation

Statistical parameters will be displayed to a defined number of decimal places as specified in the BI guideline "Reporting of clinical trials and project summaries" (10).

Tabulations of frequencies for categorical data will include all possible categories and will display the number of observations in a category as well as the percentage (%) relative to the respective treatment. Percentages will be rounded to one decimal place. The category missing will be displayed if and only if there actually are missing values. Percentages will be based on all patients in the respective patient set whether they have non-missing values or not.

Disposition of the patient population participating in the trial will be summarized by presentation of the frequency of patients screened, entered, screened but not entered, treated, entered but not treated, who completed the trial through planned visit at Week 4, who completed planned observation time, who completed trial medication, and who were prematurely discontinued, by reason. A patient is defined to have completed the trial through the planned visit at Week 4 if the patient did not discontinue the trial at any time prior to the lower bound of the week 4 time window (cf. [Table 6.7: 1](#)). The vital status of prematurely

discontinued patients at Week 20 will also be summarized. Disposition will be listed by country.

The frequency of patients with IPVs, also summarized by whether or not the IPV led to exclusion from the FAS, PPS, PKS, BMS, DSS or RSS, will be presented for the ENT-S. The frequency of patients in each of the different analysis sets will also be presented.

Baseline, for applicable analyses, refers to the last measurement collected prior to the start of administration of the trial treatment.

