### Binary efficacy endpoints

Some efficacy endpoints are defined in terms of the proportion of patients with a particular binary outcome, i.e. achievement of a GPPGA total score of 0 or 1. For those binary outcomes, the different methods for handling of missing data, presented below, will be performed as presented in Table 6.3: 1. Please note that some of these binary outcomes are derived from other parameters, but imputation is planned to take place only at the binary level, i.e., the GPPGA total score itself will not be imputed, but the binary endpoints derived based on these scores will be imputed.

- The following primary imputation strategy ("NRI") will be performed:
  - If there are data at the visits both immediately before and immediately after the visit with a missing outcome, then impute as success only if both the preceding and the following observations also represent a success (independent of whether the preceding and following observations were selected for analysis based on time windows described in [Section 6.7](#));
  - Otherwise, impute as a failure to achieve a response (i.e. no response imputation [NRI]).

For patients who take a rescue medication (as defined in [Section 5.3.4](#)) during the course of the study, all efficacy outcomes measured after the day of first use of rescue medication will be set to missing and, during the on-treatment period, will be imputed using the steps described above.

- Observed cases (OC) approach will be used as a sensitivity analysis and will include all collected data, with no imputation performed on the missing data. Such an OC approach will exclude all values measured after intake of a rescue medication (i.e. such values will be set to missing).
- Observed cases including rescue (OC-IR) approach will be used as a further sensitivity analysis and is an extension of the OC approach which includes additionally all values which were measured after rescue medication intake.

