### **7.5.2 Secondary endpoints**

#### **7.5.2.1 Secondary efficacy endpoints**

Analysis of secondary efficacy endpoints will be based on the FAS; an analysis based on the PPS will be performed as a sensitivity analysis. The analysis of imputed values (cf. [Section 6.6.2](#)) will be considered the main approach for secondary efficacy analyses of this trial. Other analysis approaches based on the FAS (and on the PPS) will be considered sensitivity analyses to assess the impact of missing data, intake of rescue medication, and IPVs on the efficacy outcomes.

The GPPASI total score and the percent reduction from baseline in GPPASI total score will be summarized descriptively by visit as will the FACIT-Fatigue scale total score and pain VAS score; the changes from baseline at each post-baseline visit will also be displayed. For the percent reduction from baseline in GPPASI total score as well as the change from baseline in FACIT-Fatigue scale total score and pain VAS at each visit, 95% confidence intervals around the mean will be presented and are calculated as follows:

$$\left( \text{mean} - t_{n-1; 0.975} \frac{SD}{\sqrt{n}}; \text{mean} + t_{n-1; 0.975} \frac{SD}{\sqrt{n}} \right),$$

where "mean" denotes the sample mean, "SD" denotes the sample standard deviation, "n" denotes the number of non-missing values in the sample, and " $t_{n-1; 0.975}$ " denotes the 0.975 quantile of the t-distribution with  $n-1$  degrees of freedom.

Graphical presentations of the mean and 95% confidence interval by visit will be provided for percent reduction from baseline in GPPASI total score, change from baseline in FACIT-Fatigue scale total score and change from baseline in pain VAS score. Additionally, for percent reduction from baseline in GPPASI total score, 95% confidence intervals for the median will be calculated based on the SAS procedure PROC UNIVARIATE with option CIPCTLDF, and graphical presentations of the median and 95% confidence interval by visit will be provided.

For the FACIT-Fatigue scale, frequencies of patients with each score for each of the individual questions will additionally be summarized by visit.

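### The all-patients denominator in SAP Section 7 stops the observed-cases GPPGA 0/1 analysis from showing how far the result depends on imputing failures

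*SAP*

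**What the plan says.** SAP Section 7, in the paragraph on frequency tables for categorical data, sets the denominator: "Percentages will be based on all patients in the respective patient set whether they have non-missing values or not". The sentence before it deals with display: "The category missing will be displayed if and only if there actually are missing values".

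SAP 6.6.2 gives three ways of handling missing binary outcomes.

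- **NRI**, the main approach. For a missing visit with data on both sides, "then impute as success only if both the preceding and the following observations also represent a success". For every other missing visit: "Otherwise, impute as a failure to achieve a response".
- **OC**, which "will be used as a sensitivity analysis and will include all collected data, with no imputation performed on the missing data". On rescue: "Such an OC approach will exclude all values measured after intake of a rescue medication".
- **OC-IR**, which is OC with the post-rescue values put back.

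Neither OC nor OC-IR is given a denominator there. SAP 7.5.2.1 says that the analyses other than the imputed one are "considered sensitivity analyses to assess the impact of missing data, intake of rescue medication, and IPVs". For the continuous endpoints the same section defines n in the confidence interval as the count of non-missing values. For the GPPGA proportion and its Wilson interval it defines no n. SAP Table 6.3: 1 lists OC as a sensitivity analysis on both the full analysis set (FAS) and the per-protocol set, and its notes do not mention denominators.

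**The concern.** The purpose of an observed-cases analysis beside NRI is to show what happens when missing outcomes are left out instead of being set to failure. The only denominator that the SAP states keeps those patients in. They add nothing to the numerator and one each to the denominator, which is what NRI does to them by default. A programmer who follows Section 7 would produce an OC percentage that repeats NRI, or is lower.

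Agreement between the two rows could then be taken as evidence that the Week 2 response rate is robust to missing data, when the agreement is built in. The label would also cover two different analyses: OC for GPPASI, FACIT-Fatigue and pain VAS drops patients without a value, while OC for GPPGA keeps them. With 6 to 10 patients planned (protocol 7.6), one or two missing values are enough to matter.

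**Working it through.** The plan states no figure to reproduce, so the check is algebra followed by assumed examples.

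**Inputs.**
- N, patients in the set: 6 to 10 (protocol 7.6).
- x, observed responders at the visit: assumed.
- m, patients with no usable value at the visit, including values removed after rescue: assumed, 0 to 3. A FAS patient can lack a Week 2 GPPGA, because one post-baseline GPPASI or GPPGA at any visit is enough for the FAS (SAP 6.3).
- b, those of the m whose neighbouring observations are both successes.

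**Formulas.**
- OC with the Section 7 denominator: x/N
- NRI: (x + b)/N
- Proportion among observed patients: x/(N − m)

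**OC against NRI.** NRI − OC = b/N, which is never negative. OC therefore cannot exceed NRI, and equals it whenever b = 0. The other m − b patients, those set to failure by default, contribute identically to both. Rescue belongs wholly in this group: every value after the day of first rescue is set to missing, so a post-rescue visit has no usable later observation, b cannot count it, and NRI makes it a failure.

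**OC against observed patients.** x/(N − m) − x/N = xm / [N(N − m)]. For N = 10, x = 5, m = 2 this is 10/80 = 12.5 points.

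Results with b = 0, so that the fourth column is both OC as written and NRI. Wilson 95% intervals use the same denominator as the percentage:

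| N | x | m | OC as written = NRI | Among observed | Gap (points) |
|---|---|---|---|---|---|
| 10 | 5 | 0 | 50.0% (23.7–76.3) | 50.0% (23.7–76.3) | 0.0 |
| 10 | 5 | 1 | 50.0% (23.7–76.3) | 5/9 = 55.6% (26.7–81.1) | 5.6 |
| 10 | 5 | 2 | 50.0% (23.7–76.3) | 5/8 = 62.5% (30.6–86.3) | 12.5 |
| 10 | 5 | 3 | 50.0% (23.7–76.3) | 5/7 = 71.4% (35.9–91.8) | 21.4 |
| 10 | 7 | 3 | 70.0% (39.7–89.2) | 7/7 = 100% (64.6–100) | 30.0 |
| 8 | 6 | 2 | 75.0% (40.9–92.9) | 6/6 = 100% (61.0–100) | 25.0 |
| 6 | 3 | 1 | 50.0% (18.8–81.2) | 3/5 = 60.0% (23.1–88.2) | 10.0 |

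With one bracketed success (N = 10, x = 5, m = 2, b = 1), NRI becomes 6/10 = 60.0% (31.3–83.2) while OC as written stays at 50.0%. That comparison shows the neighbour rule at work, but nothing about the one patient set to failure.

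**The case against.** The strongest reply is that the denominator sentence is a general tabulation rule, while OC has its own definition without imputation; a statistician could let the specific text govern and drop missing patients. That is a fair reading of intent. But the specific text gives no denominator, so the only stated rule is the one that defeats the analysis. The SAP needs to say which applies.

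Several stronger conclusions are tempting, and the documents do not support them.

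- *That every percentage in the SAP is affected.* The rule sits in the paragraph on categorical tabulations, and SAP 7.8.2 limits laboratory analyses to patients with a post-baseline value.
- *That missing patients are classified as non-responders.* They appear in their own category. Only the arithmetic of the percentage coincides, and a reader can recompute the point estimate from the displayed count or the patient listings.
- *That the sensitivity analyses carry no information.* OC below NRI exposes the neighbour-imputed successes, which are the only imputations that raise the response rate. OC-IR against OC shows the post-rescue responses, since rescued patients are to be followed to Day 140 (protocol 4.2.1.1). The continuous OC analyses already use non-missing n.
- *That the Wilson interval uses the wrong n.* Its n is not stated, so this is a gap and not a documented error.

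It is also fair to say that the observed-patient proportion is not the true response rate. Missingness caused by rescue is informative, and leaving those patients out tends to raise the percentage. This limits how OC should be read. It does not justify an OC that reproduces NRI by construction.

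**Conclusion.** The point holds in a limited form. As written, the binary OC percentage cannot exceed NRI and cannot show the effect of the default failure imputation, although SAP 7.5.2.1 gives the non-imputed analyses the task of assessing the impact of missing data. It is also inconsistent with how OC is computed for the continuous endpoints.

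The size depends entirely on missingness, which the documents do not give. In the assumed cases tabulated, with 1 to 3 patients missing, the printed OC percentage is 5.6 to 30.0 points below the proportion among observed patients; with no missing values the two agree. The endpoint is secondary and descriptive. The main NRI result and the primary safety endpoint do not change.

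**What to change.** Add one sentence to SAP 6.6.2 or 7.5.2.1, worded as an exception to Section 7: for OC and OC-IR analyses of binary efficacy endpoints, the proportion and its confidence interval use the patients in the set with a non-missing value at that visit, and n/N is shown. Keep all patients in the denominator for NRI, and state this for its Wilson interval too.

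The cost is one sentence and one programming option. The downsides are a smaller n with wider intervals in most cases, and an OC percentage that will tend to look more favourable because rescued patients leave the denominator. The text should therefore say that OC is read only as a sensitivity analysis beside NRI and OC-IR.

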## **7.1 DEMOGRAPHIC AND OTHER BASELINE CHARACTERISTICS**

Only descriptive statistics are planned for this section of the CTR.

Descriptive statistics will be presented for demographic parameters and baseline characteristics, based on the FAS. The presence of IL36RN mutation, as recorded in the eCRF at Visit 1 based on historical data, will only be listed.

For the continuous variables described below, the following categories will be defined and presented according to the number and percentage of patients in each category:

Table 7.1: 1 Categories for summary of continuous variables

Variable	Categories
Age	< 50 years 50 to < 65 years ≥ 65 years
Weight	≤ 70 kg > 70 to ≤ 80 kg > 80 to ≤ 90 kg > 90 kg
BMI	< 25 kg/m  25 to < 35 kg/m  ≥ 35 kg/m 
Time since first diagnosis	≤ 1 year > 1 to ≤ 5 years > 5 to ≤ 10 years > 10 years

## **7.2 CONCOMITANT DISEASES AND MEDICATION**

Analyses of concomitant diseases and medication will be based on the FAS.

Concomitant diseases will be coded according to the most recent version of MedDRA. Concomitant medication will be coded according to the most recent version of the World Health Organisation – Drug Dictionary.

Signs/symptoms of the trial disease (as identified on the eCRF) will be summarized separately from other concomitant diseases, by system organ class and preferred term.

Other characteristics of the trial disease, such as the frequency and percentage of resolved flares within the last 12 months, as well as details on the shortest, longest, and last GPP flare which occurred prior to admission into this trial, will be displayed. The duration (up to start of treatment) and likely cause of the current flare of GPP will also be presented. The "number of flares of GPP that resolved with treatment" will be calculated as the number of resolved flares of GPP in previous 12 months minus the number which resolved spontaneously without treatment.

A medication will be considered concomitant to treatment, if it

- is ongoing at the start of trial treatment or
- starts within the analysis phase of the trial treatment (see [Section 6.1](#) for a definition of treatments and analysis phases).

Concomitant medication use (excluding rescue medication on or after Visit 2 and before end of the on-treatment period, historical medication for GPP and background medication) will be summarized with frequency and percentage of patients by ATC3 class and preferred name. Summaries will be presented for

- concomitant therapies taken any time prior to Day 1 (the day of start of trial treatment),
- concomitant therapies initiated on Day 1, and
- concomitant therapies taken any time during the on-treatment period (cf. Section 6.1).

The frequency and percentage of patients with previous treatment on methotrexate, retinoids, cyclosporin, and other historical medication for GPP will be displayed, and will include an assessment of those patients who continue to take methotrexate or retinoids as background medication in this trial. Here, background medication is defined as any administration of methotrexate or retinoids which is ongoing on the day of administration of BI 655130. In addition, the time since last dose relative to Visit 2 for patients who have discontinued prior methotrexate or retinoid use will be listed.

Rescue medication use on or after Visit 2 and before end of the on-treatment period will be summarized separately, as described in [Section 7.6.4](#).

## **7.3 TREATMENT COMPLIANCE**

Treatment compliance will be summarized for the FAS by descriptive statistics (N, mean, SD, minimum, median, maximum) for the amount of medication taken [% of planned], and by the number and percentage of patients with

- "< 70% of planned",
- "70 to 120% of planned" and
- "> 120% of planned".

## **7.4 PRIMARY ENDPOINTS**

Refer to [Section 7.8.1](#) for a description of the analysis of AEs, and in particular the analysis of the number [N (%)] of patients with adverse reactions, defined as drug-related AEs, which is the primary endpoint of this trial.

## **7.5 SECONDARY ENDPOINT**

### **7.5.1 Key secondary endpoint**

Not applicable.

### **7.5.2 Secondary endpoints**

#### **7.5.2.1 Secondary efficacy endpoints**

Analysis of secondary efficacy endpoints will be based on the FAS; an analysis based on the PPS will be performed as a sensitivity analysis. The analysis of imputed values (cf. [Section 6.6.2](#)) will be considered the main approach for secondary efficacy analyses of this trial. Other analysis approaches based on the FAS (and on the PPS) will be considered sensitivity analyses to assess the impact of missing data, intake of rescue medication, and IPVs on the efficacy outcomes.

The GPPASI total score and the percent reduction from baseline in GPPASI total score will be summarized descriptively by visit as will the FACIT-Fatigue scale total score and pain VAS score; the changes from baseline at each post-baseline visit will also be displayed. For the percent reduction from baseline in GPPASI total score as well as the change from baseline in FACIT-Fatigue scale total score and pain VAS at each visit, 95% confidence intervals around the mean will be presented and are calculated as follows:

$$\left( \text{mean} - t_{n-1; 0.975} \frac{SD}{\sqrt{n}}; \text{mean} + t_{n-1; 0.975} \frac{SD}{\sqrt{n}} \right),$$

where "mean" denotes the sample mean, "SD" denotes the sample standard deviation, "n" denotes the number of non-missing values in the sample, and " $t_{n-1; 0.975}$ " denotes the 0.975 quantile of the t-distribution with  $n-1$  degrees of freedom.

Graphical presentations of the mean and 95% confidence interval by visit will be provided for percent reduction from baseline in GPPASI total score, change from baseline in FACIT-Fatigue scale total score and change from baseline in pain VAS score. Additionally, for percent reduction from baseline in GPPASI total score, 95% confidence intervals for the median will be calculated based on the SAS procedure PROC UNIVARIATE with option CIPCTLDF, and graphical presentations of the median and 95% confidence interval by visit will be provided.

For the FACIT-Fatigue scale, frequencies of patients with each score for each of the individual questions will additionally be summarized by visit.

The proportion of patients with a GPPGA total score of 0 (clear) or 1 (almost clear) will be summarized descriptively by visit, presenting patient frequencies and proportions together with exact 95% Wilson score confidence intervals. Additional displays of the patient frequencies and percentages for the individual GPPGA total scores (0, 1, 2, 3, 4), as well as for each subscore on the underlying characteristics ('erythema', 'pustules', and 'scaling/crusting'), will also be produced. Bar charts over time will be displayed.

The time of first achievement of a GPPGA total score of 0 (clear) or 1 (almost clear), relative to the day of start of infusion of trial treatment, will be summarized with patient frequencies and percentages for the following categories:

- No response
- Response on or after Visit 2 but prior to treatment start
- Response from treatment start to Day 4
- Response from Day 5 to Day 7
- Response from Day 8 to Day 14 (Week 2)
- Response from Day 15 to Day 28 (Weeks 3 and 4).

#### 7.5.2.2 Secondary pharmacokinetic endpoints

**CTP:** *The secondary PK parameters (refer to [CTP] Section 5.5.1) will be calculated according to the BI Standard Operating Procedure (SOP) 'Standards and processes for analyses performed within Clinical Pharmacokinetics/Pharmacodynamics' (001-MCS-36-472 [(11)]). Analyses will be performed for parent drug.*

Descriptive statistics will be presented for secondary PK endpoints, based on the PKS.

#### Exclusion of PK parameters

The ADS "ADPP" contains column variables APEXC and APEXCO indicating inclusion/exclusion (APEXC) of a PK parameter and an analysis flag comment (APEXCO). All analyses based on the PKS will include parameters if they are not flagged for exclusion, i.e. APEXC is equal to "Included".

#### Exclusion of PK concentrations

The ADS "ADPC" (PK concentrations per time point or per time-interval) contains column variables ACEXC or ACEXCO indicating inclusion/exclusion (ACEXC) of a concentration and an analysis flag comment (ACEXCO). Exclusion of a concentration depends on the analysis flag comment ACEXCO. For example, if ACEXCO is set to "ALL CALC", the value will be excluded for all types of analyses based on concentrations. If ACEXCO is set to "DESC STATS" the value will be excluded from descriptive evaluations per planned time point/time interval. If ACEXCO contains the addition "TIME VIOLATION" or "TIME DEVIATION", the value can be used for further analyses based on actual times. If ACEXCO is set to "HALF LIFE" the value will be excluded from half-life calculation only; the value is included for all other analyses.

Excluded concentrations, and concentrations and parameters of excluded patients will be listed in the clinical trial report, associated with an appropriate flag.

Further details are given in 001-MCS-36-472\_RD-01 "Noncompartmental Pharmacokinetic / Pharmacodynamic Analyses of Clinical Studies" ([5](#)) and 001-MCS-36-472\_RD-03 "Description of Analytical Transfer Files and PK/PD Data Files" ([6](#)).

